9 TREATMENT OF SUBJECTS

9.1 Treatments Administered

9.1.1 Phase 1/Phase 2 Cohorts

Part A

Cream or gel: BMX-010 0.03% or BMX-010 0.1% or Placebo QD
Cream or gel: BMX-010 0.03% or BMX-010 0.1% or Placebo BID

Part B

BMX-010 dose & formulation determined in Part A vs Placebo. QD or BID frequency as determined in Part A will be conducted.

In this study, up to 210 subjects will be enrolled.

In **Part A**, up to 60 subjects will be enrolled. Subjects will not be randomized and treatment concentration, formulation, and dosing frequency will be at the discretion of the clinical center investigator. All subjects will receive study drug at either 0.03% or 0.1% concentration. They will dose either QD or BID as indicated by the clinical center investigator during the baseline and other weekly visits throughout the study.

In **Part B**, up to 150 subjects will be enrolled. This will be a double-blind study, where the investigator and subject both will not know whether study drug or Placebo has been dispensed. Subjects will be randomized to BMX-010 or Placebo (2:1) in accordance with the randomization schedule. The Placebo cream is color-matched to the study drug, the Placebo gel is not. Up to 100 subjects will be randomized to BMX-010 and up to 50 subjects will be randomized to Placebo.

Although acne occurs on the face *and* trunk, efficacy assessment by IGA will be limited to the face as that is the most frequent site of involvement. However, the study product may be applied to all affected areas during this clinical trial.

When subjects apply QD, it can be applied any time of the day. When it is applied BID it should generally be applied 12 hours apart.

9.1.2 Blinding in Part B

The sponsor has a standard operating procedure regarding randomization and blinding. The sponsor also will have a designated list of personnel who have un-blinded access. The sites will be provided with a key to use if un-blinding is required during the trial.

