7.2 Part B Study Design

Subjects will be randomized 2:1 to receive topical administration of BMX-010 or Placebo which will be dosed at the concentration, formulation, and frequency as defined by Part A. Study product will be applied liberally to Acne Vulgaris on the face. The planned treatment duration is a minimum of 7 days and a maximum of 28 days. Completion of 28 days of treatment will be recommended to all subjects; however, subjects who have full clearing of the Acne Vulgaris, as determined by the clinical center investigator, may stop therapy and remain in the study with a final evaluation at Day 29 or Day 43 at the discretion of the investigator. There will be weekly visits with follow-up done at approximately Days 8, 15, 22, 29 and 43.

Figure 7.a Study Design for both parts

Following written informed consent, subjects will undergo screening evaluations within 14 days prior to the first application of study drug. The screening evaluations will include complete medical history, complete physical examination (including vital signs, weight, and height), clinical laboratory evaluations, urine pregnancy test for females of child-bearing potential (a negative pregnancy test is required within 48 hours prior to the start of drug treatment), concurrent medical conditions, and concomitant medication assessments.

Subjects will be scored by the clinician for IGA. The clinician will also obtain counts of the inflammatory and noninflammatory lesions on the face.

The subject will be asked a series of Patient Reported Outcomes (Appendix A).

In **Part A**, all eligible Subjects enrolled will receive the active study drug, BMX-010. Subjects will treat their Acne Vulgaris on the face with the study product. This will be demonstrated at the Baseline visit. Subjects will be instructed by the clinical center staff and informed how often they should dose each day (QD or BID).

In **Part B**, all eligible Subjects enrolled will be randomized to the study drug (BMX-010) or Placebo. Subjects will treat their Acne Vulgaris on the face with the study product. This will be demonstrated at the Baseline visit. Subjects will be instructed by the clinical center staff and informed how often they should dose each day, which will have been confirmed by Part A of the study.

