9.4 Randomization Schedule

The sponsor or designee will generate the randomization schedules. Randomization will occur once final eligibility is confirmed after completion of the screening procedures.

Part A of the study is not blinded. All subjects will receive BMX-010.

Part B of the study is double-blind, where both the subject and the clinical center staff will be blinded to the treatment assigned. BMX-010 and Placebo will be dispensed 2:1 (study drug: placebo).

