12.4 Lesion Counts

All inflammatory and noninflammatory lesions will be counted by a clinical center investigator at each weekly visit.

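### Section 9.1.2 places a Part B treatment key at sites whose staff must be blinded, and the lot-only labels and replacement rule let one legitimate code break reveal other subjects' arms

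*Protocol*

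**What the plan says.** Section 9.1.2 of the Protocol has three sentences on blinding in Part B. The first two name controls: "The sponsor has a standard operating procedure regarding randomization and blinding", and "The sponsor also will have a designated list of personnel who have un-blinded access". The third gives the sites the means to break the blind: "The sites will be provided with a key to use if un-blinding is required during the trial".

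Section 9.4 sets the blinding standard: "Part B of the study is double-blind, where both the subject and the clinical center staff will be blinded to the treatment assigned". Section 9.1.1 says the same of the investigator: "the investigator and subject both will not know whether study drug or Placebo has been dispensed". Neither section exempts an un-blinded pharmacist, coordinator or other site role.

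The centers also produce the efficacy data. Section 7.2 states: "Subjects will be scored by the clinician for IGA". Section 12.4 states: "All inflammatory and noninflammatory lesions will be counted by a clinical center investigator at each weekly visit".

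Two other sections bear on what a code break reveals. Section 9.3 labels bags and tubes by lot number and not by strength, and each bag contains a single concentration or placebo. Section 8.3 allows a withdrawn subject to be replaced by a new one, who is given the same treatment.

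**The concern.** Part B is the randomized, placebo-controlled part of the trial. Two of its primary objectives in section 6.1 are responder proportions based on an IGA grade given by the site clinician. Site principal investigators also judge whether adverse events are drug-related, which drives the stopping rules in section 7.2.1. These judgements are protected only while the person making them does not know the arm. Selection at entry is protected only while the next assignment is unknown.

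A site may have good reason to break the blind for one subject. The break should then cost the blinding of that subject and no other. Nothing in the protocol secures this. It does not say whether the key covers one subject or many, who at the site holds it, who may authorise its use, or how use is recorded. The labelling and replacement rules add two routes by which information from one break can reach other subjects.

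**Working it through.** The point needs no arithmetic. The check sets the sections side by side.

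1. **Who must be blind, and who receives the key.** Section 9.4 blinds the clinical center staff as a group. Section 9.1.2 gives the key to the sites. These are the same organisations, and section 16.1 confirms that subjects are enrolled from them. No un-blinded custodian is named.

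2. **What identifies the product.** The only identifier in section 9.3 is the lot number. The protocol mentions no kit number or subject-specific label. The composition tables in sections 9.2.2 and 9.2.3 list placebo, 0.03% and 0.1% as separate batches, so a lot very probably corresponds to one treatment. Section 9.2.5 keeps lot numbers out of the protocol because of blinding, which treats the lot as revealing.

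3. **What one legitimate opening reveals.** The protocol does not give the form of the key, so each plausible form is taken in turn:
   - *The key decodes lots.* Opening it reveals the arm of every subject on that lot, including those supplied from it later. With one active product and one lot per arm (an assumption), the other lot follows by elimination and the whole site is decoded. With several lots per arm, fewer subjects are exposed.
   - *The key lists subjects or randomization numbers.* Opening it reveals everyone listed, and future assignments too if unused numbers are included.
   - *The key is a set of sealed codes, one per subject.* Opening one reveals one subject directly. That subject's tubes still show a lot number, however, so staff can compare it with other subjects' tubes. Per-subject codes alone therefore do not limit a break to one subject while tubes are labelled by lot.

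4. **Replacement.** Section 8.3 gives the replacement the treatment of the subject who left and does not limit this to Part A. If the withdrawn subject's code was opened, the site knows the replacement's arm before accepting that person. This holds for every form of key in step 3.

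5. **Size.** At full enrolment Part B has 150 × 2/3 = 100 subjects on BMX-010 and 150 × 1/3 = 50 on placebo, which agrees with section 9.1.1. The protocol gives neither the number of lots per arm nor the number of subjects per site, so the number exposed by one break cannot be derived. Dividing 150 subjects by 20 sites gives 7.5, but both figures are maxima and the sponsor may close enrolment early, so 7.5 is not a lower bound.

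**The case against.** The strongest reply is that section 9.1.2 already has controls: a sponsor procedure on randomization and blinding, a designated list of un-blinded personnel, and use of the key only when a break is needed. Section 9.4 adds that the sponsor or its designee generates the schedule. The procedure is not shown and may well cover custody, sealing and logging. A site-held means of emergency un-blinding is compatible with blinded staff, and the protocol does not say that anyone who enrols or rates holds the key. The list is kept by the sponsor, but nothing limits it to sponsor employees. If the gel were chosen, its white placebo, which does not match the active product, would already threaten the blind, and the key would add less.

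Most of this stands, and it rules out a stronger reading. A reader might infer that the sites hold the allocation list, one key per site, and that concealment and rater blinding are unprotected. The documents do not support that. They say only that there is a key, they name some safeguards, and they show no improper access. Nor do they support a figure for bias or false-positive risk: the protocol states no significance level, response rate or effect size, and section 14.6 says sample sizes are not statistically based.

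The reply does not answer two things. An undisclosed sponsor procedure is not shown to bind the sites or to make the key subject-specific. And the lot labels and the replacement rule are written into the protocol itself, so information can pass from one properly authorised break to other subjects even if everyone follows the rules.

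**Conclusion.** The point holds as a correctable weakness, with no breach shown. The protocol places a key at blinded sites without making it subject-specific, and so does not show that one justified break leaves other subjects' blinding and concealment intact.

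The lot route rests on two inferences: that a lot corresponds to one treatment, and that the key decodes lots or staff can compare lot numbers across tubes. The replacement route needs neither. It follows from section 8.3 once a withdrawn subject's code has been opened. How many subjects are affected depends on how many codes are broken, the lots per arm and the subjects per site, none of which the protocol gives. The change is worth making because it is inexpensive and protects the investigator-rated outcomes of the randomized part.

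**What to change.** Make three linked changes for Part B.

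- **Section 9.1.2.** Replace the sentence on the key with text such as: *Sites will not hold a key covering more than one subject. Un-blinding is done for one subject at a time, through a central contact on the un-blinded list or by opening one sealed envelope for that subject. Each break is logged with date, person and reason, and reported to the sponsor. IGA scores and lesion counts recorded after a break are flagged in the database.*
- **Sections 9.3 and 9.2.5.** Label Part B supplies with subject-level kit numbers in place of a visible lot number, and keep the link from kit to lot with personnel on the un-blinded list. Without this, a single-subject break can still decode a lot.
- **Section 8.3.** Reconcile the replacement rule with concealment in Part B. Options are to give replacements a new randomized assignment, or to keep anyone who has learned the withdrawn subject's code from enrolling or rating the replacement.

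The cost is a few sentences of protocol text, kit-number labelling, and a code break that may take slightly longer than opening a key held at the site.

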9.2 Identity of Investigational Products

9.2.1 BMX-010 Drug Substance

9.2.1.1 Structure

[figure not shown]

Figure 9.1: Structure of BMX-010

9.2.1.2 General Properties

Formula Weight: 965.12

Chemical Name: Mn(III) tetrakis(*N*-ethylpyridinium-2-yl)porphyrin pentachloride

Empirical Formula: C₄₈H₄₄Cl₅MnN₈

CAS RN: 219818-60-7

Appearance: Dark brown or purple solid

9.2.1.3 Manufacturer

Drug substance Lot #9739-C-R0-01-21-01, which will be used to manufacture the clinical trial material for the presently proposed trials, was manufactured, tested and released under cGMP by Albany Molecular Research, Inc., Albany, NY (AMRI). A 3-year stability study is being performed by AMRI according to ICH guidelines.

9.2.2 BMX-010 Gel Drug Product

9.2.2.1 Description and Composition

The gel drug product is a preserved aqueous gel comprising 0.03% or 0.1% BMX-010 and having the batch composition indicated in Table 9.a. The gel is filled at 10 g/tube into 0.5 ounce white LDPE squeeze tubes with screw caps. BMX-010 is yellow/brown in color and transient (up to 7 days) of yellow discoloration of skin is not considered to be an AE.

Table 9a: Batch Composition of BMX-010 Gel

Component, Quality (Function)	Quantity per batch, g (wt%)		
	Placebo	0.03% BMX-010	0.1% BMX-010
BMX-010, AMRI (API)	—	3 (0.03%)	10 (0.10%)
Natrosol TM 250 Hydroxyethylcellulose HX, Pharm, NF (gelling agent)	300 (3.00%)	300 (3.00%)	300 (3.00%)
Propylene Glycol, USP (gelling agent)	500 (5.00%)	500 (5.00%)	500 (5.00%)
Potassium Sorbate Powder, NF (preservative)	15 (0.15%)	15 (0.15%)	15 (0.15%)
Sodium Benzoate, NF (preservative)	30 (0.30%)	30 (0.30%)	30 (0.30%)
Titanium Dioxide, USP (colorant)	200 (2.00%)	200 (2.00%)	200 (2.00%)
Glacial Acetic Acid, USP (buffer)	15.2 (0.15%)	15.2 (0.15%)	15.2 (0.15%)
Sodium Hydroxide 1N solution, USP (buffer)	164.4 (1.64%)	164.4 (1.64%)	164.4 (1.64%)
Sterile Purified Water, USP (solvent)	8775.4 (87.75%)	8772.4 (87.72%)	8765.4 (87.65%)
Medical Air, USP (blowing agent)	0	0	0
Total batch weight	10000	10000	10000

9.2.3 BMX-010 Cream Drug Product

9.2.3.1 Description and Composition

The cream drug product is a preserved oil-in-water emulsion cream comprising 0.03% or 0.1% BMX-010 and having the batch composition indicated in Table 9.a. The cream is filled at 10 g/tube into 0.5 ounce white LDPE squeeze tubes with screw caps. BMX-010 is yellow/brown in color and transient (up to 7 days) of yellow discoloration of skin is not considered to be an AE.

Table 9a: Batch Composition of BMX-010 Cream

Component, Quality (Function)	Quantity per batch, g (wt%)		
	Placebo	0.03% BMX-010	0.1% BMX-010

BMX-010, AMRI (API)	—	1.8 (0.03%)	6 (0.10%)
Mineral Oil, NF (emollient)	720 (12.00%)	720 (12.00%)	720 (12.00%)
Petrolatum, USP (emollient)	540 (9.00%)	540 (9.00%)	540 (9.00%)
Cetostearyl alcohol, NF (emollient, viscosity increasing agent)	720 (12.00%)	720 (12.00%)	720 (12.00%)
Propylene glycol, USP (humectant)	480 (8.00%)	480 (8.00%)	480 (8.00%)
Glacial Acetic Acid, USP (buffer)	9 (0.15%)	9 (0.15%)	9 (0.15%)
Sodium Hydroxide 1 N solution, NF (buffer)	102.6 (1.71%)	102.6 (1.71%)	102.6 (1.71%)
Sterile Purified Water, USP (solvent)	3,236.4 (53.94%)	3276.6 (54.61%)	3272.4 (54.54%)
Tween 20-LQ-(AP) (emulsifier)	60 (1.00%)	60 (1.00%)	60 (1.00%)
Isopropyl palmitate, NF (emollient, viscosity increasing agent)	60 (1.00%)	60 (1.00%)	60 (1.00%)
Imidazolidinyl urea, NF (preservative)	12 (0.20%)	12 (0.20%)	12 (0.20%)
Methylparaben, NF (preservative)	12 (0.20%)	12 (0.20%)	12 (0.20%)
Propylparaben, NF (preservative)	6 (0.10%)	6 (0.10%)	6 (0.10%)
Iron Oxides, NF (colorant)	42 (0.7%)	—	—
Medical Air, USP (blowing agent)	0	0	0
Total batch weight	6000	6000	6000

9.2.4 Manufacturer

The drug product will be manufactured, tested and released under cGMP by Velesco Pharmaceutical Services, LLC, Kalamazoo, MI (Velesco). Stability adequate to support the proposed clinical study of the BMX-010 gel and cream will be demonstrated by Velesco. Stability studies will be conducted in accordance with ICH Q1A (R2) using a cGMP qualified stability indicating analytical method.

9.2.5 Labeling

The drug product labels will include a brief description of the drug product, the sponsor, lot number, storage information, emergency contact, and the statement, "Caution: New Drug – Limited by Federal Law to Investigational Use." Lot numbers are not listed in the protocol as Phase 2 studies using the cream will be double-blinded.

BMX-010 Gel or Cream –Lot X
BioMimetix JV, LLC
Caution: New Drug – Limited by Federal
Law to Investigational Use
Emergency contact: [name],
cell [contact] Store at RT or
Refrigeration

Exemplary Label BMX-010 – Depending if the study product is a cream or gel, this will dictate the storage instructions. The gel is stored at room temperature and the cream is stored under refrigerated conditions.

9.2.6 Placebo

Placebo (vehicle) will consist of the same excipients as the active drug product, but without the API. The placebo gel is white in color and does not match the color of the active drug. The placebo cream is color-matched to facilitate blinding. Placebo will be supplied in 10 mL tubes.

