Part B is a randomized, double-blind, multi-center, placebo-controlled study of adult men and women with Acne Vulgaris. Subjects will be randomized and dosed with BMX-010 0.03% or 0.1% with the frequency of dosing (either QD or BID) for each dose of the study drug as determined optimal in Part A of this trial. Dosing will occur for a minimum of 7 days and a maximum of 28 days. An overview of the study design is presented in the schematics below, and details of study activities are provided in **Table 4a**.

In the Part A study, up to a total of up to 60 evaluable subjects with Acne Vulgaris will be dosed with BMX-010 (0.03% or 0.1%) topically applied either QD or BID. All subjects will dose for a minimum of 7 days and a maximum of 28 days. The dosing strength, formulation, frequency, and time frame will be at the discretion of the local clinician.

The sponsor may close enrollment once enough data has been obtained to determine the optimal dosing frequency and duration of dosing for each concentration (0.03% or 0.1%) of BMX-010 cream or gel to be studied in Part B.

In the Part B study, up to 150 evaluable subjects with Acne Vulgaris will be dosed with the concentration and formulation of BMX-010 determined optimal in Part A or Placebo given at the frequency determined optimal in Part A. The randomization scheme is 2:1, study drug : Placebo. All subjects will dose for a minimum of 7 days and a maximum of 28 days.

The sponsor may close enrollment once enough data has been obtained to assess the expected efficacy of 0.03% BMX-010 and 0.1% BMX-010. This data will be used to plan future studies.

The Investigator Global Assessment (IGA) is a five scale (0 to 4) static evaluation of overall Acne Vulgaris severity (as described below).

Investigator Global Assessment (IGA) Scale

Grade	Description
0 = Clear	Clear skin with no inflammatory or noninflammatory lesion
1 = Minimal	Almost clear, rare noninflammatory lesions with no more than one small inflammatory lesion
2 = Mild	Mild, some noninflammatory lesions, no more than a few inflammatory lesions
3 = Moderate	Moderate, up to many noninflammatory lesions and may have some inflammatory lesions, but no more than one small nodular lesion
4 = Severe	Severe, up to many noninflammatory and inflammatory lesions, but no more than a few nodular lesions

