The Placebo will consist of a formulation containing the same excipients as the active drug product. The Placebo will be color-matched to the active study drug. Placebo will be supplied in 10 mL tubes. Formulation and packaging of the Placebo is done by Velesco Pharmaceutical Services, LLC.

Criteria for Evaluation:

Clinical Efficacy

Clinical effectiveness will be evaluated using the Five-scale IGA for Acne Vulgaris at baseline and end of study, Patient-reported outcomes, and counts of inflammatory and noninflammatory lesions.

Safety Assessments

Safety will be assessed via AE monitoring, concomitant medication monitoring, physical examinations, vital signs, clinical safety laboratory evaluations (complete blood count and chemistry), and pregnancy testing (if applicable).

Table 4.a Schedule of Observations and Procedures

Assessment	Screening ⁷	Treatment Period						Follow-up	
	Day -14 to Day -1	Baseline Day 1	Day 8 (+/- 2 days)	Day 15 (+/- 2 days)	Day 22 (+/- 2 days)	Day 28 ⁸	Day 29 (+/- 2 days)	Day 43 (+/- 2 days)	Follow-up ⁹
Informed consent	X								
Inclusion/exclusion criteria	X	X							
Medical history/demographics	X								
Concurrent medical conditions	X	X	X	X	X		X	X	
Medication history	X								
Concomitant medications	X	X	X	X	X		X	X	
Physical examination, including vital signs and weight ¹	X	X	X	X	X		X	X	
Height	X								
IGA ²	X	X	X	X	X		X	X	
Lesion Counts (Face)		X	X	X	X		X	X	
PRO questions ³			X	X	X		X	X	
Clinical safety laboratory assessments ⁴		X						X	
Urine pregnancy test ⁵	X							X	
Randomization *Part B only		X							
Dosing ⁶		X	X	X	X	X			
Discoloration Review			X	X	X		X	X	
Photographs (optional)		X	X	X	X		X	X	
Pre- and post-treatment AE monitoring	X	X	X	X	X		X	X	

¹ Includes sitting blood pressure, pulse rate and temperature.

² IGA is the 5-point scale as defined in this protocol.

³ All subjects will be asked questions regarding the study drug, clearing and color, these are the Patient Reported Outcome (PRO) questions (see Appendix A).

⁴ Clinical safety laboratory assessments will include CBC with differential and CMP.

⁵ Females of child-bearing potential must have negative results within 48 hours prior to start of drug treatment for inclusion. The Day 43 test is performed for females of child-bearing potential who receive at least one application of study drug.

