6 STUDY OBJECTIVES

6.1 Primary Objectives

Part A

1. Determine whether the optimum frequency of topical application of BMX-010 0.03% is once per day or twice per day for a treatment interval of 7 to 28 days.
2. Determine whether the optimum frequency of topical application of BMX-010 0.1% is once per day or twice per day for a treatment interval of 7 to 28 days.
3. Determine if BMX-010 cream or gel provides better efficacy.
4. Evaluate the efficacy of BMX-010 0.03% in treatment of Acne Vulgaris.
5. Evaluate the efficacy of BMX-010 0.1% in treatment of Acne Vulgaris.

Part B

1. Evaluate the efficacy of BMX-010 compared to placebo in a randomized, double-blind trial.
2. Determine the percent of subjects showing a 2 grade improvement in IGA score after treatment with BMX-010 compared to Placebo.
3. Determine the percent of subjects showing a 2 grade improvement in IGA score with full or partial clearing (final IGA score of 1 or 0) after treatment with BMX-010 compared to Placebo.
4. Determine the time to full clearing of Acne Vulgaris after initiation of treatment with BMX-010.

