7 STUDY DESIGN

The purpose of this study is to first explore the optimum formulation (gel vs. cream), concentration (0.03% vs. 0.1%), and dosing frequency (QD vs. BID) of BMX-010 in subjects with Acne Vulgaris in Part A. In Part B, the optimal formulation, concentration, and frequency will be used to study the efficacy of BMX-010, as determined by IGA scores and PROs.

[figure not shown]

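### Part B is declared double-blind, yet the gel placebo is white and unmatched, and the protocol leaves gel open for Part B without saying how the colour difference would be masked

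*Protocol*

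**What the plan says.** **On blinding.** The Synopsis calls Part B double-blind. Section 9.1.1 describes a study "where the investigator and subject both will not know whether study drug or Placebo has been dispensed", and Section 9.4 repeats it: "Part B of the study is double-blind, where both the subject and the clinical center staff will be blinded to the treatment assigned". None of these statements depends on the formulation.

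**On the placebo's colour.** The Synopsis, under Placebo, says: "The Placebo will be color-matched to the active study drug". Section 9.1.1, in the same paragraph that declares the blind, says: "The Placebo cream is color-matched to the study drug, the Placebo gel is not". Section 9.2.6 agrees with 9.1.1: "The placebo gel is white in color and does not match the color of the active drug". Sections 9.2.2.1 and 9.2.3.1 describe BMX-010 as yellow/brown.

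**On the formulation for Part B.** A Part A primary objective in Section 6.1 reads: "Determine if BMX-010 cream or gel provides better efficacy". Section 7 says that in Part B "the optimal formulation, concentration, and frequency will be used to study the efficacy of BMX-010, as determined by IGA scores and PROs". Section 7.2 takes the formulation from Part A, and the Synopsis describes the dosing decision as one made "for each concentration (0.03% or 0.1%) of BMX-010 cream or gel to be studied in Part B".

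**On masking measures.** Section 9.1.2 refers to a sponsor procedure on randomization and blinding, a list of unblinded personnel and an unblinding key for the sites. Section 9.3 says labels carry the lot number but not the strength. Section 9.2.5 mentions double-blinding in connection with Phase 2 studies that use the cream.

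**The concern.** The Synopsis and Sections 9.1.1 and 9.2.6 cannot all be right about the placebo's colour. The consequence is more than editorial: the protocol allows a Part B in which the declared blind cannot be delivered with the placebo it describes.

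Part B efficacy rests on the IGA, which is a clinician's grade, and on the subject's own answers. With gel, the subject applies the product every day and would see white or yellow/brown. Section 7.2 has study staff supervise the first application and has subjects bring their tubes to weekly visits, so centre staff would see it too. Appendix A also asks subjects whether the product's colour concerns them. Subjects and staff who know or guess the arm may score differently, and that difference cannot afterwards be separated from a drug effect.

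**Working it through.** **1. Is gel really open for Part B?** Three places say so: the Synopsis names cream or gel for Part B, Section 6.1 makes the comparison a Part A primary objective, and Sections 7 and 7.2 carry the preferred formulation forward. The only text pointing the other way is Section 9.2.5, which links double-blinding to the cream. That sentence explains why lot numbers are left out of the protocol; it does not exclude gel.

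**2. Do the batch tables confirm the colour mismatch?**

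Gel (Section 9.2.2.1). The components other than drug and water are identical in the three batches: 300 + 500 + 15 + 30 + 200 + 15.2 + 164.4 = 1,224.6 g.

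| Gel batch | Common components (g) | Water (g) | Drug (g) | Total (g) |
|---|---|---|---|---|
| Placebo | 1,224.6 | 8,775.4 | 0 | 10,000 |
| 0.03% | 1,224.6 | 8,772.4 | 3 | 10,000 |
| 0.1% | 1,224.6 | 8,765.4 | 10 | 10,000 |

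The differences in water are 8,775.4 − 8,772.4 = 3.0 g and 8,775.4 − 8,765.4 = 10.0 g, exactly the weight of drug. So the placebo gel contains no matching colorant. The 2% titanium dioxide is in all three batches.

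Cream (Section 9.2.3.1). The common components sum to 2,721.6 g.

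| Cream batch | Common components (g) | Water (g) | Drug (g) | Iron oxides (g) | Total (g) |
|---|---|---|---|---|---|
| Placebo | 2,721.6 | 3,236.4 | 0 | 42 | 6,000 |
| 0.03% | 2,721.6 | 3,276.6 | 1.8 | 0 | 6,000 |
| 0.1% | 2,721.6 | 3,272.4 | 6 | 0 | 6,000 |

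Only the cream placebo contains iron oxides, 42/6,000 = 0.7%. Colour matching was therefore done for the cream alone, as Sections 9.1.1 and 9.2.6 say. As a minor consequence, the statement in the Synopsis and Section 9.2.6 that placebo and active share the same excipients does not fit the cream.

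**3. Do the stated masking measures cover the gel?** A label without strength, a list of unblinded staff and a code-break key do not conceal the colour of what comes out of the tube. The sponsor's procedure is cited but not reproduced, so its content cannot be checked.

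**4. How many subjects?** At 2:1, 150 × 2/3 = 100 active and 150 × 1/3 = 50 placebo. With gel, the colour is visible for all of them.

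**5. How much could it matter?** The protocol gives no response rate, test or alpha, and Section 14.6 says the sample sizes have no statistical basis. The following is therefore illustration only, and every input except 100 versus 50 is assumed: no true effect, a pooled two-proportion z-test at two-sided 5%, true response of 10%, 20% or 30%, and knowledge of the arm adding a fixed number of percentage points to the active responder rate. The chance of a significant result in favour of the drug, by exact binomial enumeration, is:

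| Shift towards active | True response 10% | 20% | 30% |
|---|---|---|---|
| 0 points | 2.0% | 2.3% | 2.4% |
| 3 points | 6.5% | 5.7% | 5.4% |
| 5 points | 11.9% | 9.5% | 8.6% |
| 10 points | 33.7% | 25.4% | 22.1% |

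**The case against.** The strongest reply is that the harm is conditional. The blind fails only if Part A selects gel, the Synopsis says Part A will inform the design of Part B, and Sections 9.2.5 and 9.2.6 suggest that blinding was planned around the cream. That is fair, and the conclusion is stated conditionally. But an intention that is not written down does not bind the Part B decision, and the gap has to be closed before that decision is carried out.

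Second, general blinding measures do exist. This also stands, so the criticism is limited to the absence of any stated measure for the gel's colour.

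Third, no section says that the person grading the IGA sees the product. That is correct: exposure of the subject is certain, exposure of centre staff follows from the supervised first dose, and exposure of the rater is likely but inferred. A rater kept away from the product would help, but the subject would still be unblinded.

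Fourth, the treatment stains skin. Section 10.2 expects discoloration in more than 30% of subjects, and centre staff grade it at the weekly visits (Section 12.5). Some unmasking may therefore occur with either formulation. It is a separate residual risk, is not counted here, and does not justify adding a difference visible in every subject.

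Finally, the percentages in the illustration have no source in the protocol. Agreed; the finding does not depend on them.

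**Conclusion.** The point holds and should be fixed before Part B starts. The contradiction between the Synopsis and Sections 9.1.1 and 9.2.6 is certain, and so is the lack of any restriction of Part B to a matched formulation. The loss of the blind depends on gel being chosen, which cannot be known from the protocol. In that case product colour differs by arm for all of the up to 150 subjects, on outcomes open to expectation bias. The size of that bias cannot be derived. Under the assumed inputs above, a 5-point shift would raise false findings for the drug from about 2% to between 9% and 12%. If cream is chosen, there is no product-colour mismatch and the remaining errors are of wording, with the skin-discoloration risk still present.

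**What to change.** 1. State in Sections 7.2 and 9.2.6 that Part B may use only a formulation for which a colour-matched placebo exists. At present that is the cream. If Part A favours gel, require a colour-matched gel placebo to be prepared and released before the first Part B subject is randomized, so that the Part A comparison of formulations is not overridden.
2. Bring the Synopsis (Study Design and Placebo) and Sections 7.2, 9.1.1, 9.2.5 and 9.2.6 into agreement, and qualify the Synopsis sentence on colour matching.
3. As a clerical correction, say in the Synopsis and Section 9.2.6 that the excipients are the same apart from the colorant used for matching.

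With cream, the cost is text edits only. With gel, it is a new placebo batch with release and stability work (compare Section 9.2.4) and a possible delay to Part B. Neither route adds subjects, and neither is shown to remove the risk of unmasking through skin discoloration.
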